7.2. Safety Endpoints

- Adverse Events (AE) graded by NCI-CTCAE v4.0 system
- Serious AE (SAE)
- Death, if any
- Vital signs
- Laboratory tests
- Physical examination
- 12-lead ECG

7.3. Covariates

The analyses of the primary and secondary endpoints will be performed using the following randomization stratification factor as covariate:

- Age (<18, \geq 18 years of age)

Analyses of a given continue endpoint will also include its corresponding baseline as a covariate.

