#### 5.2.2 Observation while in emergency department

To start immediately after administration of study medication:

- Intake and output hourly:
  - all oral and parenteral intake

- urination: number of voidings
  - vomiting: number of episodes
  - stool output: number, consistency (per scale in original protocol and per Bristol Stool Scale, Appendix I)
- Vital signs at least hourly and just prior to discharge: temperature, blood pressure, pulse, respiratory rate
- Questioning regarding adverse events: hourly and just prior to discharge
- Assessments of nausea: on signing informed consent, just prior to first dose of study medication, hourly, just prior to discharge from emergency department. A 5-point Likert scale will be used:
  - 0 No nausea
  - 1 Mild nausea
  - 2 Moderate nausea
  - 3 Severe nausea
  - 4 Nausea as bad as can be

- 12-lead ECG 4±0.25 hours after initial dose of study medication (regardless of whether dose was repeated in ED). If patient leaves ED <4 hours after dosing, an ECG should still be obtained just prior to discharge.
- Brief physical examination of pertinent systems prior to discharge

If a patient vomits ≥30 minutes after taking the first dose of study medication, requires rescue antiemetic or parenteral hydration, he or she will be considered a treatment failure. The patient will be followed according to the schedule above for a total of 4 hours from the time of first administration of study medication or until discharged home, whichever comes first. After that, for patients still in the emergency department or hospital, the patient will be followed per standard protocol, according to the patient's condition.

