## 7. Data Analysis and Statistical Considerations

### 7.1 Sample Size Considerations

The primary endpoint is a composite of the following three parameters from 30 minutes until 24 hours after the first dose of study medication:

- absence of vomiting
- no use of rescue medication, and
- no intravenous hydration

If all of the above three criteria are fulfilled, the patient is considered a treatment success for the primary analysis. If one or more of the above three criteria are not fulfilled, i.e., the patient either experiences vomiting, receives rescue medication or receives intravenous hydration from 30 minutes through 24 hours after the first dose of study medication, the patient is considered a treatment failure.

It is expected that approximately 40% of the placebo group will fail treatment during the 24 hours after initial dosing and that RHB-102 will reduce the incidence of treatment failure by approximately 50%, i.e., to an incidence of 20% in the active treatment group. Patients will be stratified by age (<18,  $\geq$ 18 years of age) and randomized 60:40 to active versus placebo. To demonstrate a statistically significant decrease in the incidence of vomiting with a 2-tailed p-value=0.01 and power=90%, 320 patients will be entered into the study, 192 randomized to RHB-102 and 128 to placebo.

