9.2. Analyses of Primary Endpoint

Primary efficacy analysis will be based on the ITT population. The primary endpoint will be tested by Cochran Mantel Haenszel (CMH) test stratified by age. Common odds ratio and its 95% confidence interval will be provided. If the observed 2-sided p-value from the CMH test is

less than 0.05, statistical significance will be declared. Point estimates of the proportions for each treatment arm will be provided along with the corresponding 2-sided 95% confidence intervals. The point estimate of the difference of the proportions between treatment arms will also be provided along with corresponding 2-sided 95% confidence intervals.

For the above primary analysis, Patients who drop out of the study and patients who have unknown primary endpoint will be imputed as failures/non-responders, as stated in the handling of missing value section above.

As a sensitivity analysis, patients who drop out of the study and patients who have unknown primary endpoint will be imputed as responders. The primary analysis of CHM by age will be repeated.

One additional sensitivity analysis, the most conservative approach, will have following imputations:

- patients who drop out of the study and patients who have unknown primary endpoint in active arm will be imputed as failures/non-responders
- patients who drop out of the study and patients who have unknown primary endpoint in placebo arm will be imputed as responders

In addition, subgroup analyses by each age group (<18 , ≥ 18 years of age) will be conducted. For a given age group, unstratified CMH test will be performed. Furthermore, subgroup analyses by baseline nausea severity will also be conducted. None and mild severity will be combined as one group. For a given severity group, unstratified CMH test will be performed.

Primary analysis will also be performed on Subgroup Population 1 and Subgroup Population 2.

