9. LOGISTIC REGRESSIONS

Per final SAP, the primary endpoint was analyzed and tested by using Cochran Mantel Haenszel (CMH) test stratified by age. In order to adjust for covariates, logistic regressions will be used in this supplemental SAP.

In this section, all logistical regression analyses will be performed for both ITT population and Subgroup Population 1.

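### The primary test is valid but adjusts for age group only; pre-dose nausea, scheduled for every patient, enters an adjusted analysis only after unblinding

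*SAP*

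**What the plan says.** **Covariates.** SAP 7.3: "The analyses of the primary and secondary endpoints will be performed using the following randomization stratification factor as covariate". The one factor listed is age, below 18 v 18 and over. The same section adds an endpoint's own baseline value only for continuous endpoints, so the binary primary endpoint gets no baseline severity term. SAP 9.2 and Protocol 7.4.2 both specify a CMH test stratified by age, with significance at two-sided 0.05.

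**The score.** Protocol 5.2.2 schedules "Assessments of nausea: on signing informed consent, just prior to first dose of study medication", then hourly and at ED discharge, on a five-level scale from none to as bad as can be.

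**Use of the score before unblinding.** SAP 9.2: "Furthermore, subgroup analyses by baseline nausea severity will also be conducted". None and mild are pooled, which leaves four groups, each tested by an unstratified CMH. No overall estimate adjusted for nausea is planned.

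**Use of the score after unblinding.** SAP version 4.0 was signed on June 1, 2017 and the study was unblinded on June 3. The supplemental SAP is dated June 23. Its section 9 states: "In order to adjust for covariates, logistic regressions will be used in this supplemental SAP". It lists four models, each fitted in the ITT population and in Subgroup Population 1. Section 9.1 uses age group, 9.2 continuous age, 9.3 nausea, and 9.4 continuous age plus nausea. Only 9.3 and 9.4 include nausea.

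**The concern.** Baseline nausea is a plausible prognostic factor for this endpoint. Protocol 4.2 allows rescue medication for severe nausea from 30 minutes after dosing, and rescue alone makes a patient a treatment failure. A patient with worse nausea before dosing may be more likely to reach that point. The score costs nothing extra to collect, and its grouping was already fixed in SAP 9.2.

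Leaving it out of the primary test has two consequences. Any precision it would add is lost, and a chance imbalance between arms stays in the primary estimate. Subgroup tests do not replace an adjusted overall estimate, because each uses only part of the sample.

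Timing limits any later repair. The SAP was revised on May 18 and May 29, 2017, and it states that no unblinding took place before revision, so a covariate could have been added then. Adjusted p-values first specified after unblinding cannot carry confirmatory weight, and with several models in two populations a reader cannot tell which one was meant to count.

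**Working it through.** **Inputs from the documents.** Protocol 7.1 expects that "approximately 40% of the placebo group will fail treatment during the 24 hours after initial dosing", falling "to an incidence of 20% in the active treatment group", with patients "randomized 60:40 to active versus placebo". The size is set "with a 2-tailed p-value=0.01 and power=90%, 320 patients will be entered into the study, 192 randomized to RHB-102 and 128 to placebo". The decision level is 0.05 two-sided (Protocol 7.4.1, SAP 5.1).

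**Reproducing the sample size.** With a pooled variance and ratio 1.5, the mean rate is (0.40 + 1.5×0.20)/2.5 = 0.28.

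- Placebo n = [2.576×√(0.28×0.72×(1+1/1.5)) + 1.282×√(0.24+0.16/1.5)]² / 0.20² ≈ 127
- Active n = 1.5 × this, rounded up = 191; total 318, against 320 stated

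At 192/128 the power is 90.4% at 0.01 and 97.2% at the 0.05 decision level.

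**Assumptions not in the documents.** Failure odds ratio per nausea level of 1, 1.5, 2 or 3; nausea levels 5/10/25/40/20%; 15% of patients under 18; odds ratio 1.35 for adults v adolescents. For orientation, a logit slope of 0.5 per level (odds ratio e^0.5 ≈ 1.65), with nausea levels 5/15/35/30/15%, corresponds to placebo failure from about 17% with no nausea to about 60% at the worst level.

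**Simulated power at 0.05.** 4,000 trials per scenario at 192/128, with marginal failure rates held fixed. Each cell shows CMH by age, then CMH by age × four nausea groups.

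| Odds ratio per level | 40% v 20% | 40% v 25% | 40% v 28% |
|---|---|---|---|
| 1 | 97.5 → 97.2 | 81.6 → 81.0 | 62.4 → 61.8 |
| 1.5 | 97.2 → 97.4 | 81.9 → 82.1 | 61.1 → 61.7 |
| 2 | 97.3 → 98.1 | 82.2 → 84.9 | 61.3 → 64.2 |
| 3 | 97.1 → 98.8 | 81.7 → 87.4 | 60.5 → 67.2 |

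The Monte Carlo standard error of each figure is at most about 0.8 points, so the smallest differences should not be read closely. With 35% failure in both arms, type I error at 0.05 is 4.8 to 5.1% for the age-only test and 4.6 to 5.2% for age × nausea.

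**Cost if nausea is not prognostic.** A stratum of size n contributes information in proportion to n − 1, so the total is N minus the number of strata. Age alone gives 320 − 2 = 318. Age × nausea gives 320 − 8 = 312. The ratio is 312/318 = 0.98, or about 2% of effective sample size lost.

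**Chance imbalance.** With nausea levels assumed at 5/15/35/30/15%, the SD is 1.06 levels; the distribution used for the power table gives 1.07.

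- SD of the difference in mean level between arms = 1.06×√(1/192+1/128) = 0.121, so 2 SD = 0.24 of a level
- At a logit slope of 0.5, risk changes per level by about 0.5×0.24 = 0.12 on placebo and 0.5×0.16 = 0.08 on active, about 0.10 on average
- Shift in the unadjusted difference ≈ 0.24×0.10 = 0.024, or about 2 points
- Standard error of the difference = √(0.24/128+0.16/192) = 0.052

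A 2-point shift is 0.020/0.052 ≈ 0.4 of a standard error. A steeper gradient would raise it roughly in proportion.

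**The case against.** The strongest reply is that nothing is broken. The CMH test stratified by the only randomization factor is prespecified, identical in protocol and SAP, and holds its error rate. Chance imbalance is already allowed for in that error rate, and it would be visible in the baseline summaries (SAP 9.1) and in the nausea subgroups fixed before unblinding. All of this stands. A reader might infer that the age-only result is biased or invalid; the documents and the simulated type I error do not support that.

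The prognostic strength is also assumed. The protocol's ground for rescue is severe nausea after dosing, not before, so the link is indirect. This stands too, and is why the size is given as a range that includes a small loss.

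Two more readings go too far. A reader might work at 0.01, where the simulated gain at 40% v 20% reaches 3.8 points (91.2% to 95.0% at an odds ratio of 3 per level). That is the sample-size level; the primary decision is taken at 0.05. A reader might also take the score as complete for every patient. The protocol only schedules it, and completeness is not reported.

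Finally, the supplement discloses the unblinding date, calls its analyses additional to those planned, and does not offer the models as a replacement for the CMH test. That is fair. It does not, however, label each model post hoc or say how the set is to be read.

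**Conclusion.** The point holds as a missed, nearly free gain in precision, not as an error in the primary test. At the planned effect the change in power is small, about -0.3 to +1.7 points. It becomes material, up to about +7 points, only if the true effect is smaller (40% v 28%) and nausea is strongly prognostic. Both conditions are assumptions. An imbalance as large as 2 SD would move the difference by about 2 points under a middle gradient, roughly 0.4 of its standard error.

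It may be tempting to promote supplement model 9.4 in ITT as the one adjusted sensitivity analysis and call only the others post hoc. The documents do not support that distinction. Model 9.4 was also written after unblinding. It enters age and nausea as continuous terms, so it matches neither the randomization stratum nor the four groups of SAP 9.2. Its odds ratio is conditional on different variables from the age-stratified common odds ratio, so the two are not directly comparable.

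**What to change.** **If the blind is intact:** in SAP 7.3 and 9.2, name the score taken just before the first dose as baseline, since two pre-dose scores are scheduled, and state a rule for a missing value. Group it as none/mild, moderate, severe, and as bad as can be. Run the primary CMH test and a Mantel-Haenszel risk difference by age × nausea, and keep the age-only CMH as supportive. The cost is SAP wording, a few sparse cells, which the CMH test tolerates, and about 2% of effective sample size if nausea turns out not to be prognostic.

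**If the study is already unblinded, as the supplement records:** leave the age-stratified CMH as primary, because changing it now would itself be open to influence from the data. Label every logistic model in supplement section 9 post hoc, including 9.4, and report all of them in both populations so that none is selected by its p-value. This costs wording only. In a further trial, specify the nausea stratum before unblinding.

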9.3. Efficacy Analyses for Secondary and Tertiary Endpoints

ITT population will be used for the analyses of all secondary and tertiary endpoints.

1) Analyses of Binary/Proportion Endpoint

Same statistical test as for the analyses of the primary endpoint, as stated in Section 9.2, will be used for analyzing other proportion endpoints.

2) Analyses of Time-to-Event Endpoints

Time to event endpoints will be compared between the treatment arms using stratified log-rank test adjusting the age stratification factor. The endpoints will also be summarized using the Kaplan-Meier method and displayed graphically when appropriate. Median event times and 2-sided 95% confidence interval for each median will be provided.

3) Analyses of Continuous Endpoints

Descriptive statistics, including the mean, standard deviation, median, minimum, and maximum values, will be provided for continuous endpoints.

4) Analyses of Ordinal Categorical Endpoints

The number and percentage of patients in each category will be provided for categorical endpoints. Bristol Stool Scale (BSS), added in the Protocol Amendment 3, is an 8 point ordinal categorical variable. Wilcoxon rank sum test will be used to compare the two treatment groups.

5) Concordance Assessment of Bristol Stool Scale and Stool consistency

Stool consistency, as recorded per original protocol, none/formed (normal)/soft/watery (diarrhea), is a 4 point ordinal categorical variable. Cross-tabulation of stool consistency and BSS among all the patients who have both assessments at a given time point will be created to evaluate the concordance of the two scales. Cohen's Weighted Kappa Coefficient and 95% confidence interval will be provided.

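### SAP 9.3 specifies no method that carries out the covariate rules of SAP 7.3 for non-binary, non-time endpoints, so severity of nausea is compared without its pre-dose score or the age stratum

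*SAP*

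**What the plan says.** SAP 7.3 sets two rules. The first concerns age (under 18, 18 and over): "The analyses of the primary and secondary endpoints will be performed using the following randomization stratification factor as covariate". The second concerns baseline values: "Analyses of a given continue endpoint will also include its corresponding baseline as a covariate" (continue evidently means continuous).

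SAP 9.3 then gives methods by type of endpoint. Binary endpoints take the age-stratified CMH test, and time-to-event endpoints take a log-rank test stratified by age. For continuous endpoints, item 3 says: "Descriptive statistics, including the mean, standard deviation, median, minimum, and maximum values, will be provided for continuous endpoints". For ordinal endpoints, item 4 says: "The number and percentage of patients in each category will be provided for categorical endpoints". It then introduces the Bristol Stool Scale (BSS), and the next sentence is: "Wilcoxon rank sum test will be used to compare the two treatment groups".

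Severity of nausea is a secondary endpoint in Protocol 2.2 and 7.4.4 and is listed in SAP 7.1. Protocol 5.2.2 describes its collection in the ED: "Assessments of nausea: on signing informed consent, just prior to first dose of study medication, hourly, just prior to discharge from emergency department". On the scale it says: "A 5-point Likert scale will be used", running from 0 to 4. The SAP does not say whether the endpoint is continuous or ordinal, which time point is compared, or which pre-dose score is the baseline.

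**The concern.** Section 7.3 makes a commitment that the methods in 9.3 cannot keep. A covariate needs a model or a stratified test to enter. Items 3 and 4 provide neither, whereas items 1 and 2 do use the age stratum.

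Nausea is where this matters most. It has a pre-dose score on the same scale as the outcome, collected in the ED at no extra effort. Starting severity is usually among the strongest predictors of later severity, so leaving it out gives up precision. It also leaves the comparison open to whatever imbalance in starting nausea chance produces. In addition, with hourly ED scores and, for patients sent home as successes, three diary scores a day, the analyst is left to choose the time point, summary and test.

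**Working it through.** The plan states no figure for nausea. Its sample size (192 RHB-102, 128 placebo) was set for the binary primary endpoint. The check is therefore mainly a comparison of text, followed by an illustration of size.

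**1. Rule against method for nausea**

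| If nausea is | Baseline rule in 7.3 | Age rule in 7.3 | Method in 9.3 | Uses baseline? | Uses age? |
|---|---|---|---|---|---|
| continuous | applies | applies | item 3: summary statistics | no | no |
| ordinal | does not apply | applies | item 4: counts, perhaps Wilcoxon | no | no |

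The age rule goes unmet in both rows. The baseline rule is contradicted only in the first. The pre-dose score is unused in both.

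**2. Where baseline nausea is used**

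- SAP 9.2: subgroups for the primary endpoint.
- Supplemental SAP 9.3 and 9.4: covariate in logistic models of the primary endpoint.
- Supplemental SAP 14: correlation with age.
- Supplemental SAP 13: Kaplan-Meier analysis of time to no nausea, censored at rescue or IV fluid. No baseline term is stated.

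So the pre-dose score serves the primary endpoint but not the nausea endpoint itself.

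**3. Size, under assumptions**

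The documents give no standard deviation, effect or correlation for nausea. Let r be the correlation between pre-dose and later nausea, assumed to lie between 0.3 and 0.6. In a linear model, adjustment multiplies residual variance by 1 - r².

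- r = 0.3: 1 - 0.09 = 0.91, a 9% cut. The interval is narrower by 1 - √0.91 = 5%.
- r = 0.6: 1 - 0.36 = 0.64, a 36% cut. The interval is narrower by 1 - √0.64 = 20%.

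The same loss can be seen as chance imbalance. With 192 and 128 patients, the standard error of the difference in mean pre-dose score, in SD units, is √(1/192 + 1/128) = √0.01302 = 0.114. A difference of up to 1.96 × 0.114 = 0.22 SD is then within the 95% range of chance. Unadjusted, it would shift the nausea difference by 0.3 × 0.22 = 0.07 SD to 0.6 × 0.22 = 0.13 SD. This restates the variance loss and does not add to it.

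For an assumed standardised difference of 0.3 at two-sided 0.05, power is Φ(0.3 / (0.114 × √(1 - r²)) - 1.96): 0.75 unadjusted, 0.79 at r = 0.3 and 0.86 at r = 0.5.

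These are linear-model figures and approximate for a 0-4 score. In a proportional-odds model the gain appears as power, not as a smaller standard error.

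**The case against.** The strongest reply is that the baseline rule covers continuous endpoints only, and nausea is most naturally ordinal. SAP 9.3 calls the 8-point BSS and the 4-point stool consistency scale ordinal, and a 5-point Likert score is of the same kind. On that reading the baseline sentence in 7.3 may be unused boilerplate that could simply be deleted. This part stands: a reader might infer that the SAP breaks its own baseline rule for nausea, and the text does not establish that. The supplemental SAP does enter baseline nausea as a continuous covariate, but that is coding of a covariate in a document written after unblinding and does not classify the endpoint.

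The reply does not reach the age rule, which covers secondary endpoints of every type. Nor does it show that an unadjusted comparison is the better choice when the pre-dose score is already in hand.

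Other points on that side also stand. A rank test in a randomised trial is valid. Item 3 is silent about tests and does not forbid them. The Wilcoxon sentence follows the one on the BSS, so it may not cover nausea at all. The supplemental Kaplan-Meier analysis does give a comparison with p-values. If the main SAP's log-rank rule carries over to it, that comparison is stratified by age, though the supplement does not say so.

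**Conclusion.** The point holds as a mismatch between SAP 7.3 and 9.3, and as a missed improvement at little cost for one secondary endpoint. However it is classed, severity of nausea is compared in the main SAP without its pre-dose score and without the age stratum. The later supplemental analysis states no baseline term either.

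The consequence is limited to precision and chance imbalance. On assumed correlations of 0.3 to 0.6 the residual variance would fall by about 9% to 36% in a linear model. The text mismatch does not depend on those assumptions.

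Three stronger readings are not supported:

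- **That the nausea comparison is biased.** Randomisation rules out systematic bias, and the primary CMH test is untouched.
- **That baseline nausea is ignored throughout.** It is used for the primary endpoint.
- **That adjustment is worth 352 to 500 patients** (320/0.91 and 320/0.64). This applies assumed correlations and a linear model to a sample size set for a binary endpoint, and takes every patient to have usable nausea scores.

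**What to change.** In SAP 9.3:

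- Class severity of nausea as ordinal.
- Compare it at a fixed ED time, for example the hourly assessment at 4 hours, with a proportional-odds model (or ANCOVA) that has treatment, age stratum and pre-dose nausea as terms.
- Name the score just before the first dose as the baseline.
- State how scores after rescue medication or IV fluid are handled, and scores of patients who leave before the chosen time.
- Keep the descriptive tables.

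A fixed time is preferable to the last ED assessment, which falls at different times and can follow rescue. An ED time is preferable to the diary. Under Protocol 5.2.3, patients who fail within 24 hours have only one later call, so diary scores are selectively missing.

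Then align SAP 7.3: say which endpoints the age and baseline rules cover, or remove what no method carries out. Deleting the baseline sentence alone would leave the age rule unmet for items 3 and 4.

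The cost is SAP wording and one model, with no new data. SAP 4.0 was signed on June 1, 2017 and the study was unblinded on June 3, 2017, so a model added after that date must be labelled post hoc.
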